- ii. Blood ketones – The study will be cancelled if the blood ketones are $> 1 \text{ mmol/L}$. If blood ketones are $> 1 \text{ mmol/L}$, a venous blood sample will be sent to the central lab at Emory University for a basic metabolic panel, venous pH and beta-hydroxybutyrate to rule out diabetic ketoacidosis. If diabetic ketoacidosis is confirmed, the subject will be stabilized per the usual routine care at Emory Healthcare.
- iii. Blood glucose prior to insertion of Dexcom G6 CGM's and intravenous lines – The subjects Reference Glucose Value must be in the range of 70-300 mg/dL prior to insertion of the two Dexcom G6 CGM's and two intravenous lines.

In addition, the closed loop glucose control session of the study will not be initiated if the participant has symptoms requiring action (e.g., abdominal pain, vomiting, unable to eat or drink, fever ≥ 101.5), regardless of blood glucose or ketone levels.

3. Dexcom G6 CGM devices

The subjects will have two Dexcom G6 CGM devices placed in the abdominal position, approximately 5 cm to the left or right of the umbilicus (Figure 25).

[figure not shown]

Figure 25 – Green shaded areas denote appropriate areas of the abdominal wall to place the Dexcom G6 CGM's. This figure is from the Dexcom G6 CGM user manual.

The CGM devices should be placed shortly after arrival to the CRC facility. For the Dexcom G6 CGM labeled "#1", enter the glucose sensors four-digit code and the transmitters six-digit serial number into the Dexcom G6 Receiver labeled "#1" and into the Dexcom G6 Follow App on the mobile phone labeled "#1". For the Dexcom G6 CGM labeled "#2", enter the glucose sensors four-digit code and the transmitters six-digit serial number into the Dexcom G6 Receiver labeled "#2" and into the Dexcom G6 Follow App on the mobile phone labeled "#2". Position the mobile phones 15-20 feet from the bed the subject will be using during the study.

4. Peripheral Intravenous Lines

For purposes of medication infusion, all subjects will have a peripheral IV placed into the antecubital vein of one arm. For purposes of blood removal, all subjects will have an IV placed in the contralateral hand in a retrograde position. The hand with the retrograde IV will be warmed to 50-55 degrees Celsius with a commercial warming box or warming pad for purposes of arterializing the venous blood.⁹⁰

5. Reference Glucose Value

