After both Dexcom CGM's have started to return glucose values to the Dexcom Receivers, and prior to starting the closed loop glucose control portion of study, a Reference Glucose Value(s) (taken from arterialized retrograde hand IV line) will be measured using the Nova StatStrip Hospital Glucose Meter System. If the retrograde hand vein is no longer available at any point during visit 3, Reference Glucose Values may be obtained from a finger stick (capillary blood), with analysis of this sample being performed on the Nova StatStrip Hospital Glucose Meter System.

On July 12, 2018, the FDA cleared the Nova StatStrip Hospital Glucose Meter System for point of care capillary blood glucose monitoring for all hospital patients, specifically including those receiving intensive medical intervention therapy. According to the FDA's 510(k) Substantial Equivalence Determination Decision Summary Assay and Instrument Combination Template for this product, two

studies were performed. In the first study for blood glucose values less than 75 mg/dL, 1 of 1 specimen (100%) was compliant, and for blood glucose values greater than or equal to 75 mg/dL, 484/567 (85.4%) specimens were compliant. In the second study for blood glucose values less than 75 mg/dL, 1614/1894 (85.2%) specimens were compliant, and for blood glucose values greater than or equal to 75 mg/dL, 12799/14884 (86.0%) specimens were compliant.⁹¹

The Nova StatStrip Hospital Glucose Meter System has been cleared for use on arterial, venous, and capillary whole blood samples, and is currently used to guide intravenous insulin infusion rates in the ICU setting.

6. Calibration of Dexcom G6 CGM's

The Dexcom G6 CGM's will be calibrated under the following scenarios:

1. The Dexcom G6 CGM value(s) do not meet CGM Validation Criteria

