Prior to starting the closed loop glucose control session, a Reference Glucose Value will be obtained immediately after the time when the CGM sensors begin to return glucose readings. Reference Glucose Values will be subsequently checked every 30 minutes until the CGM sensor values meet the following CGM Validation Criteria:

1. CGM's must be within 20 mg/dL of the Reference Glucose Value for CGM values less than 100 mg/dL, or within \pm 20% of the Reference Glucose Value for CGM values greater than or equal to 100 mg/dL.

Closed-loop therapy will begin after two consecutive averages of CGM values meet the above CGM Validation Criteria. The above CGM Validation Criteria will be used throughout the entirety of visit 3.

Blood for independent glucose analysis will be drawn from the retrograde venous line in the warmed hand. The drawn blood will be immediately analyzed for glucose using the Nova StatStrip Hospital Glucose Meter System. These blood glucose values will be known as the Reference Glucose Values. If the arterialized venous line stops working, it may be replaced. If an arterialized venous line is no longer available, fingerstick capillary blood may be used for Reference Glucose Values. Fingerstick capillary blood will be analyzed using the Nova StatStrip Hospital Glucose Meter System.

All Reference Glucose Values will be manually recorded on the studies case report form, however, they will not be used by the FUSION system for purposes of glucose control (except to calibrate the Dexcom G6 CGM's, as necessary).

All subjects will be allowed to drink water throughout the course of the study. No glucose containing drinks will be allowed during the closed loop portion of the study, unless the subjects glucose level (CGM or Reference Glucose Value) is < 70 mg/dL, or the subject is experiencing symptoms of neuroglycopenia. Subjects will remain confined to either the bed or a bedside chair throughout the course of the study. Subjects will use a bedside commode for bathroom breaks in order to prevent any interruption to their closed loop glucose control session.

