| 11. | 
Two IV Catheters placements:
 
 - One antecubital intravenous line (for infusion of insulin and dextrose) with an 18-20 gauge catheter with two 3-way gang stopcock (insulin from FUSION system in first stopcock, dextrose from FUSION system in second stopcock). First stopcock closest to subject, second stopcock furthest from subject. - One IV (18-20 gauge catheter) in contralateral hand (from antecubital IV) placed in a retrograde fashion for purposes of blood draws. This hand to be warmed as noted below. - Study nurse to inspect IV sites on an hourly basis, or whenever subject complains of pain at IV site. - A. Run $\frac{1}{2}$ normal saline at 10 mL/hr using a standard IV pump through the IV line used to infuse insulin and/or dextrose from the FUSION system. B. Run normal saline at 10 mL/hr using a standard IV pump through the retrograde hand IV line used for blood draws. |
| 12. | 
Warming of retrograde hand vein to 50-55 °C
 
Arm with retrograde hand IV that is to be used for blood sampling will be kept warm by use of a heating pad or similar device to increase blood flow in order to achieve “arterialized” samples.⁹³
 |
| 13. | 
Monitoring Activities:
 
A. Vital signs (Every 4 hours throughout the entire CRC stay): Temp _____ RR _____ HR _____ Time of collection: _____:_____
 
BP _____ / _____ Time of collection: _____:_____
 
Document the vital signs on the case report form.
 
B. Assessment of IV sites (Every 1 hour during closed loop glucose control session): Assess for signs of infiltration as evidenced by local swelling or pain at IV insertion site. Assess for signs of bleeding. Document these assessments on the case report form.
 
C. Assessment for fluid overload (Every 2 hours during closed loop glucose control session): Assess for signs of fluid overload that will be manifested as peripheral edema (swelling of hands, feet, legs, or eyelids), shortness of breath, and rales on auscultation of lungs. Document these assessments on the case report form.
 
D. Assessment of CGM insertion sites (Every 4 hours from time 4 to 32 hours): Assess for local signs of skin irritation, bleeding, or infection.
 
E. Assessment for development of DKA, Severe Hyperglycemia, or HHS
 |

| | |
|-----|--|

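### The 50-55 °C warming figure is given for the hand or hand vein, a heating pad is allowed, and no pad or skin limit is set; taken literally or as a pad setting, it is an unsafe contact temperature

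*Combined protocol and SAP*

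**What the plan says.** Two places in the combined document give a warming temperature for the blood-sampling hand.

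- Section 8.1.1.4, item 4 (Peripheral Intravenous Lines): "The hand with the retrograde IV will be warmed to 50-55 degrees Celsius with a commercial warming box or warming pad". The stated purpose is to arterialize the venous blood.
- Protocol 2 (IMT2022-1-P2), item 12, heading: "Warming of retrograde hand vein to 50-55 °C". The text below it reads "Arm with retrograde hand IV that is to be used for blood sampling will be kept warm by use of a heating pad", or with a similar device, and gives no number.

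Sampling relies on this line. Section 8.1.1.4 describes the Reference Glucose Value before closed loop as "taken from arterialized retrograde hand IV line", and adds: "Blood for independent glucose analysis will be drawn from the retrograde venous line in the warmed hand". A fingerstick is allowed if the line is lost. In the recovery period (Protocol 2, item 20), either a venous catheter sample or a fingerstick may be used for both diabetes types, whether or not the line still works.

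The hand is observed regularly. Protocol 2, item 11: "Study nurse to inspect IV sites on an hourly basis, or whenever subject complains of pain at IV site". Item 13B, hourly during the closed loop: "Assess for signs of infiltration as evidenced by local swelling or pain at IV insertion site. Assess for signs of bleeding". Item 13C, every 2 hours during the closed loop, covers "peripheral edema (swelling of hands, feet, legs, or eyelids") among the signs of fluid overload.

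**The concern.** In both places the temperature is attached to the hand or the vein, and in both a contact device is allowed. A nurse following the page has one number to work with and could set a pad against skin to 50-55 °C for many hours, including overnight. The nurse would be at the bedside at least hourly, but the listed signs would not point to redness or blistering of the heated hand. A burn would be an avoidable harm from a supporting procedure, unrelated to the device under test.

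**Working it through.** The plan has no figure of its own to reproduce here. The check is a comparison of the relevant places, plus a unit conversion and an estimate of exposure time.

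**1. What the temperature applies to.**

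| Place | Object of 50-55 °C | Device allowed | Pad setting, skin limit or time limit |
|---|---|---|---|
| Section 8.1.1.4, item 4 | the hand | box or pad | none |
| Protocol 2, item 12, heading | the hand vein | (see text) | none |
| Protocol 2, item 12, text | arm kept warm, no figure | heating pad or similar | none |

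Neither place calls the figure a device setting or a box-air temperature. The room equipment in section 8.1.1.4, item 1, and the materials list in Protocol 1 name neither a warming device nor a skin-temperature probe. Staff could not measure hand or vein temperature with the listed materials, which makes it more likely that the figure would be used as a device setting.

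**2. Scale of the figure.** °F = °C × 9/5 + 32, so 50 °C = 122 °F and 55 °C = 131 °F. Against an assumed body temperature of 37 °C, the excess is 50 − 37 = 13 °C to 55 − 37 = 18 °C.

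**3. Possible exposure.** The documents do not state how long the hand is warmed. Sampling times give a guide.

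- Clock (Protocol 2, item 8): 0800 is time 1 and 1200 is time 5, so 0900 is time 2.
- Start of warmed-hand sampling: time 2 (the 0900 example in section 8.1.1.5) or time 4 (Protocol 2, item 15).
- Before the closed loop: 5 − 4 = 1 h to 5 − 2 = 3 h.
- Closed loop: 29 − 5 = 24 h.
- Sum: 24 + 1 = 25 h to 24 + 3 = 27 h.
- If warming continued to the earliest line removal (time 32, Protocol 2, item 21): 32 − 4 = 28 h to 32 − 2 = 30 h, and longer if glucose is not yet stable.
- Shorter if fingersticks replace the line or the session stops early.

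**4. Safeguards.** Item 11's hourly inspection has no stated end, so it covers the hours outside the closed loop when 13B is not scheduled. The signs named in 13B are swelling, pain and bleeding. Item 13D, by contrast, asks for skin irritation at the CGM sites; no such request is made for the heated hand. Heat injury is not among the risks named in section 4 or the termination criteria in section 9.1 and Protocol 2, item 14. No rule says when to stop warming.

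**The case against.** The strongest reply is that the documents show an ambiguity and not an unsafe procedure. Both places cite published work on arterialized sampling, and blood drawing is referred to the research center's own methods (section 4.1; Protocol 2, item 18). A box-air meaning or a local pad setting may be found there. With no probe listed, nobody could in practice bring a vein to 50-55 °C, and the instruction under item 12 says only to keep the arm warm. Subjects must be able to communicate, pain at the site triggers an inspection, adverse events are recorded whatever their cause, and a safety monitor reviews them. No endpoint analysis depends on the point.

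Much of this stands. A reader might infer that subjects will be burned, or that the site's actual practice is unsafe. The documents do not support either: they give no burn threshold and do not show how the site applies the figure. A reader might also infer that warming must last 28-30 h. That does not follow, because item 20 allows fingersticks throughout recovery and warming need not extend past time 29. Nor is the hand unobserved, given the hourly inspections.

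The reply does not remove the printed figure. Sources outside the document do not override an explicit number in it. A box-air meaning would not carry over to the pad that section 8.1.1.4 offers as an alternative and that item 12 names. Pain is a useful prompt, but less so in a sleeping subject, and an inspection finds an injury only after it has begun. It does not replace a temperature limit.

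**Conclusion.** The concern holds as a point about the stated instruction. The protocol gives 50-55 °C as a hand or hand-vein temperature, allows a heating pad, and sets no pad or skin limit. Followed literally, or used as a pad setting, that is an unsafe contact temperature.

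It applies to all eight planned subjects, for about 25-27 h if the hand is warmed from the first line samples to the end of the closed loop. Because duration is unstated, that span is neither an upper nor a lower limit. The chance of a burn cannot be estimated from these documents.

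The conclusion rests on two assumptions: general clinical knowledge that prolonged skin contact at this temperature can injure, and that no local procedure outside these documents supplies a lower limit. The text should be corrected because the possible harm is avoidable and the correction is cheap.

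**What to change.** In section 8.1.1.4, item 4, and Protocol 2, item 12 (heading and text):

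1. Delete 50-55 °C as a temperature of the hand or vein.
2. If the investigators confirm that box air was meant, say that the figure applies only to the air in a commercial warming box, and never to a pad in contact with skin.
3. For a pad, require a separate, lower maximum setting fixed by the investigators, or remove the pad option. The documents offer no value, so none is proposed here.

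Add redness, blistering or burn of the warmed hand to the existing hourly IV-site check for as long as the hand is warmed. If any is seen, stop warming and use fingersticks, which the protocol already accepts as a source of Reference Glucose Values.

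The cost is wording in two places and one line in an existing check. Samples may be somewhat less arterialized. The primary endpoints use the glucose data that drive the controller, so Reference values reach them only through CGM calibration; the Clarke error grid uses Reference values directly.

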4.3.12 RISK OF HYPEROSMOLAR HYPERGLYCEMIC SYNDROME

HHS is defined as a serious complication in subjects with type 2 diabetes, and occasionally in subjects with type 1 diabetes, that occurs when the subject experiences severe hyperglycemia (usually >600 mg/dL) for a prolonged period of time. HHS may produce severe dehydration, altered level of consciousness, and coma. The risk of subjects developing HHS while they are in the study is expected to be low and will be mitigated close monitoring of the subject's Reference Glucose Values at least every 1 hour with the Nova StatStrip Hospital Glucose Meter. If the subject has a CGM value greater than 240 mg/dL (detected by CGM alarm set for glucose values > 240 mg/dL) or Reference Glucose Value greater than 240 mg/dL, the risk will be further mitigated by monitoring the subjects Reference Glucose Value every 30 minutes until their Reference Glucose Value is less than 240 mg/dL. Finally, the risk will be mitigated by terminating the study if the subjects CGM or Reference Glucose Value remains > 300 mg/dL for more than 1 hour.

The overall risks of the study are outweighed by the potential benefit of demonstrating the safety of the FUSION systems AI based glucose control software, which is the first step in testing this software with an eventual goal of using it to create a closed loop glucose control system for use in the ICU setting.

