9 STUDY INTERVENTION DISCONTINUATION AND PARTICIPANT DISCONTINUATION/WITHDRAWAL

9.1 DISCONTINUATION OF STUDY INTERVENTION ON INDIVIDUAL SUBJECT

In the context of this study, termination is defined as the act of bringing either the study on one subject, or the entire study to a permanent end.

On each subject the study will be immediately terminated for any of the following reasons:

A. Termination Criteria for individual subjects:

The study will be terminated on individual subjects if any of the following criteria are met:

1. Subject or their legal authorized representative requests withdrawal from the study for any reason.
2. The clinical study nurses are unable to insert two working Dexcom G6 CGM's prior to beginning the closed loop glucose control session.
3. Subject has a Reference Glucose Value less than 54 mg/dL.
4. Subject has signs of prolonged severe hyperglycemia, as defined by Reference Glucose Value > 240 mg/dL for more than 2 hours.
5. Subject has signs of DKA, as defined by a Reference Glucose Value > 240 mg/dL and blood ketones > 1 mmol/L.
6. CGM or Reference Glucose Value remains > 300 mg/dL for more than 1 hour.
7. FUSION system has only one Dexcom G6 CGM available for use for more than 4 hours.
8. FUSION system has no Dexcom G6 CGM's available for use for more than 20 minutes.
9. There are no Reference Glucose Values for a period of time greater than 60 minutes.
10. The FUSION system experiences any unanticipated adverse device effect (UADE).
11. The subject has had more than 2% of their estimated total blood volume drawn during visit 3.
12. The FUSION system delivers more than 2000 mL (insulin and dextrose infusions) during the 24-hour closed loop glucose control session.

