DEMONSTRATION OF AN ARTIFICIAL INTELLIGENCE BASED CLOSED LOOP GLUCOSE CONTROL SYSTEM AS A THERAPEUTIC MODALITY IN TYPE 1 AND TYPE 2 DIABETIC PATIENTS

Protocol IMT 2022-1

CONFIDENTIAL

Version1.0.7

[figure not shown]
22 August 2022

To avoid risk to our human subjects, vital signs will be monitored closely. Frequent independent glucose measurements will be performed (every 10-60 minutes) to minimize the risk of severe hypoglycemia (< 54 mg/dL) or moderate hypoglycemia (54-69 mg/dL) with the above noted hypoglycemia symptoms. The protocol calls for rescue doses of 15 mL of 50% dextrose for severe hypoglycemia, moderate hypoglycemia with hypoglycemia symptoms, or neuroglycopenia. In addition, the study on any one subject will be terminated if they experience a severe hypoglycemia event (< 54 mg/dL). The overall study will be terminated if two subjects experience a severe hypoglycemia event (< 54 mg/dL).

Patients with a history of liver failure, renal failure, cerebrovascular accident, seizure disorder, congestive heart failure, and ischemic heart disease will not be recruited for this study.

During the time period when the FUSION system is operational and active, if a participant's CGM or Reference Glucose Value is >240 mg/dL for over 1 hour or ≥ 300 mg/dL at any point after starting the FUSION system, the following steps will be taken: Ketones will be assessed at the discretion of the principal investigator(s) for any concern about possible ketosis or DKA by checking a blood ketone level at the bedside. If the blood ketone level is greater than 1 mmol/L, a venous blood sample from the subject will be sent to the central laboratory of Emory Healthcare for a basic metabolic panel, blood pH, and beta hydroxybutyrate level. If the subject is found to be in DKA, the subject will be stabilized per the usual routine care at Emory Healthcare.

When a hyperglycemia/ketotic event meets the above reporting requirements, an Adverse Event Form will be completed. Events meeting DKA criteria should be considered serious adverse events with respect to reporting requirements. Hyperglycemia events not meeting criteria for DKA generally will not be considered as serious adverse events unless one of the severe adverse event criteria is met.

| Meal Challenge Protocol Detailed | | | | | | | | | |
|--|---|------|-----------------------------|-----------|----|-------|----|--------|----|

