| 14. | 
Termination Criteria
 
A. Termination Criteria for individual subjects:
 
The study will be terminated on individual subjects if any of the following criteria are met:
 
1. Subject requests withdrawal from the study for any reason.2. The clinical study nurses are unable to insert two working Dexcom G6 CGM's prior to beginning the closed loop glucose control session.3. Subject has a Reference Glucose Value less than 54 mg/dL.4. Subject has signs of prolonged severe hyperglycemia, as defined by Reference Glucose Value > 240 mg/dL for more than 2 hours.5. Subject has signs of DKA, as defined by a Reference Glucose Value > 240 mg/dL and blood ketones > 1 mmol/L.6. Subject has signs of HHS, as defined by a Reference Glucose Value > 300 mg/dL for more than 1 hour.7. FUSION system has only one Dexcom G6 CGM available for use for more than 4 hours.8. FUSION system has no Dexcom G6 CGM's available for use for more than 20 minutes.9. There are no Reference Glucose Values for a period of time greater than 60 minutes.10. The FUSION system suffers any unanticipated adverse device effect (UADE).11. The subject has had more than 2% of their estimated total blood volume drawn during visit 3.12. The FUSION system delivers more than 2000 mL (insulin and dextrose infusions) during the 24-hour closed loop glucose control session. 
B. Termination Criteria for the entire study:
 
The entire study will be terminated if the following criteria are met:
 
1. Two subjects experience Reference Glucose Values < 54 mg/dL during the time period the FUSION system is in use.2. Two subjects experience an episode of severe hyperglycemia, as defined by a Reference Glucose Value > 240 mg/dL for more than 2 hours.3. One subject experiences an episode of DKA after starting the closed loop glucose control session.4. One subject experiences an episode of HHS after starting the closed loop glucose control session.5. The FUSION system delivers more than 2000 mL (insulin and dextrose infusions) during the 24-hour closed loop glucose control session in two subjects.6. The FUSION system experiences any unanticipated adverse device effect (UADE).7. The study's principal investigator determines that the safety of the studies subjects is being compromised through use of the FUSION system. |

| | |
|-----|---|

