| 15. | 
Obtain Reference Glucose Values using the Nova StatStrip Hospital Glucose Meter System every 10-60 minutes from time 4 to 32 hours according to the following guidelines:
 
A. Every 10 minutes: Monitor the subject's Reference Glucose Values every 10 minutes whenever either of the following occur:
 
I. Either of the Dexcom G6 CGM's is less than 70 mg/dL.II. When the most recent Reference Glucose Value is less than 70 mg/dL. 
Discontinue every 10 minute Reference Glucose Value monitoring when both of the following have occurred:
 
I. Both Dexcom G6 CGM's are greater than 70 mg/dL.II. The subjects have two consecutive Reference Glucose Values greater than 70 mg/dL. These Reference Glucose Values will be measured by the Nova StatStrip Hospital Glucose Meter System on either a venous or capillary blood sample. 
B. Every 30 minutes: Monitor the subject's Reference Glucose Values every 30 minutes when the following occur:
 
I. After both Dexcom G6 CGM's begin to return glucose readings after their original insertion and prior to the onset of the closed loop glucose control session, for purposes of verifying the accuracy of the CGM's. This monitoring prior to the onset of the closed loop glucose control session may be discontinued once both CGM's have met the following CGM Validation Criteria on two consecutive Reference Glucose Values: 
CGM readings must be within ± 20 mg/dL of the Reference Glucose Value for CGM readings < 100 mg/dL or CGM readings must be within $\pm 20\%$ of Reference Glucose Values for CGM readings ≥ 100 mg/dL on two consecutive Reference Glucose Values.
 
II. During the first 2 hours of the closed loop glucose control session (time 5-7 hours).III. When either Dexcom G6 CGM has a glucose reading less than 85 mg/dL displayed on either the Dexcom G6 Receiver or the Dexcom G6 Follow App.IV. During periods of severe hyperglycemia, which is defined as a CGM or Reference Glucose Value greater than 240 mg/dL.V. When only one Dexcom G6 CGM is available for use by the FUSION system for glucose control.VI. After a CGM has been replaced, and until the replaced CGM has met the above noted CGM Validation Criteria.VII. When the subject experiences any signs of neuroglycopenia, regardless of the glucose level displayed by the CGM's.VIII. From time 29-32 hours, which is the 3 hour time period after conclusion of the closed loop glucose control session. |

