|-----|---|

| | |
|-----|--|
| | 
C. Every 60 minutes: Monitor the subject's Reference Glucose Value every 60 minutes when the following occur:
 
During the last 22 hours of the closed loop glucose control session (time 7-29 hours), if the following occur:
Both CGM's are in the range of 85-240 mg/dL and the subject is not experiencing any signs of neuroglycopenia. 
Result: _____ mg/dL, Time: _____ (24 hour clock) Note: Notify study team if the CGM or Reference Glucose Value is < 70 mg/dL or > 300 mg/dL.
 |
| 16. | 
Dexcom G6 CGM Placement, Calibration and Replacement
 
Visit 3 (Time 0 to 5 hours): Place two Dexcom G6 CGM's in the abdomen 5 cm to the right and left of the umbilicus (Figure 28).
  
18 years and older
 
Figure 28 – Green shaded areas denote appropriate areas of the abdominal wall to place the Dexcom G6 CGM's. This figure is from the Dexcom G6 CGM user manual.
 |

Make sure the Dexcom G6 Transmitters are labeled “#1” and “#2”. These labels should be in a clearly visible position after the Transmitters have been attached to the Dexcom G6 glucose sensors. Once both Dexcom CGM’s begin to return glucose values, obtain a Reference Glucose Value using the Nova StatStrip Hospital Glucose Meter System. If either of the Dexcom CGM’s do not meet CGM Validation Criteria, they may be calibrated. The Dexcom G6 CGM’s must meet the following CGM Validation Criteria throughout the CRC study session (visit 3), otherwise they will be calibrated as often as is necessary:

1. CGM readings must be within ± 20 mg/dL of the Reference Glucose Value for CGM readings < 100 mg/dL or CGM readings must be within $\pm 20\%$ of Reference Glucose Values for CGM readings ≥ 100 mg/dL on two consecutive Reference Glucose Values.

Calibrations should only be attempted when the glucose rate of change is less than ± 2 mg/dL/min on the Dexcom G6 CGM (see figure 29).

If after two calibration attempts prior to beginning the closed loop glucose control session (time 0-5 hours) the CGM(s) still do not meet CGM Validation Criteria, they may be replaced. The closed loop glucose control session may not begin until there are two working Dexcom G6 CGM’s in place, and both CGM’s have met the above noted CGM Validation Criteria.

Closed Loop Glucose Control Session (Time 5 to 29 hours):

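### The single-subject stop for glucose above 300 mg/dL for more than 1 hour counts CGM or Reference readings in 9.1 and 4.3.12, but Reference only in the Protocol 2 bedside list, which also labels it as HHS

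*Combined protocol and SAP*

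**What the plan says.** Three current statements describe the same single-subject stop.

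- Section 9.1, item 6: "CGM or Reference Glucose Value remains > 300 mg/dL for more than 1 hour".
- Section 4.3.12, as a mitigation of HHS risk: "terminating the study if the subjects CGM or Reference Glucose Value remains > 300 mg/dL for more than 1 hour".
- Protocol 2 (IMT2022-1-P2), item 14A.6: "Subject has signs of HHS, as defined by a Reference Glucose Value > 300 mg/dL for more than 1 hour".

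Section 4.3.12 describes HHS as what occurs when a subject "experiences severe hyperglycemia (usually >600 mg/dL) for a prolonged period of time". Section 9.2 item 4 and Protocol 2 item 14B.4 end the entire study after one subject has an episode of HHS.

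These related rules bear on the same readings:

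- Both lists (9.1 item 4 and 14A.4) share a Reference-only stop: "Subject has signs of prolonged severe hyperglycemia, as defined by Reference Glucose Value > 240 mg/dL for more than 2 hours".
- Protocol 2 item 15B.IV calls for Reference checks every 30 minutes: "During periods of severe hyperglycemia, which is defined as a CGM or Reference Glucose Value greater than 240 mg/dL".
- The note to item 15 reads: "Notify study team if the CGM or Reference Glucose Value is < 70 mg/dL or > 300 mg/dL".
- Section 4.3.10 requires a ketone screen once CGM or Reference exceeds 240 mg/dL. The Potential Problems text of Protocol 2 leaves ketone testing to the principal investigator's discretion when "CGM or Reference Glucose Value is >240 mg/dL for over 1 hour or ≥ 300 mg/dL at any point after starting the FUSION system".
- Section 8.1.1.4 item 6 calls for recalibration when a CGM of 100 mg/dL or more differs from Reference by more than 20%.

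**The concern.** This is a mandatory safety stop, and the two lists that staff would consult do not agree on what sets it off. Protocol 2 is the step-by-step worksheet for the visit. A nurse following it could keep running a session that 9.1 has ended. No clause says which list prevails.

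The label is a second ambiguity. Item 14A.6 attaches HHS to a level of 300 mg/dL, half the usual level in 4.3.12. Elsewhere the documents give HHS only that descriptive figure, while an HHS episode in one subject closes the study.

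No sample size or error rate is involved. What is at stake is consistent handling of a safety event and, secondarily, how many glucose values a subject contributes. There are eight subjects, all who start are analysed (11.3), and none who start may be replaced (9.2).

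**Working it through.** The plan gives no figure to reproduce. The check asks whether the rules can diverge with an acceptable sensor, and for how long.

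**Can they diverge?** A CGM of 100 mg/dL or more is acceptable up to 1.20 times Reference. At CGM 301, Reference can be as low as 301 / 1.20 = 250.8 mg/dL. Example: CGM 310 and Reference 270 give 310 / 270 = 1.148, or 14.8% high, so no recalibration is due. After an hour 9.1 ends this session and 14A.6 does not.

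**Upper bound.** Let t = 0 when CGM passes 300, and let L be the minutes for which Reference has already been above 240.

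- 9.1 item 6 fires at t = 60.
- The shared stop (14A.4) fires at t = 120 − L, if Reference stays above 240.
- If Reference levels off between 240 and 300, 14A.6 never fires and the gap is max(0, 60 − L). L = 0, 30 and 60 give 60, 30 and 0 minutes.

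The 60-minute ceiling needs Reference to pass 240 only as CGM passes 300. Those exact values give a ratio of 300 / 240 = 1.25, outside tolerance. With a valid sensor and smoothly changing glucose, the ceiling is therefore approached rather than reached. At 30-minute checks, 60 minutes spans at most two scheduled Reference measurements.

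**Steady rise.** Assume Reference rises at v mg/dL/min and CGM/Reference is a constant r. Reference then passes 300 as well, so 14A.6 also fires:

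- 14A.6 at t = 60 + (300 − 300/r)/v
- 14A.4 at t = 120 − (300/r − 240)/v
- gap = the earlier of these two times, minus 60

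| r | Reference when CGM = 300 | Gap, v = 1 | Gap, v = 2 |
|---|---|---|---|
| 1.05 | 285.7 | 14.3 min | 7.1 min |
| 1.148 | 261.3 | 38.7 min | 19.3 min |
| 1.20 | 250.0 | 50.0 min | 25.0 min |

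At v = 1 the two Protocol 2 stops coincide, because 60 − (300/r − 240) equals 300 − 300/r. At v = 2, 14A.6 comes first and sets the gap.

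**Which statement is the outlier?** Of the three statements of this stop, two use CGM or Reference and one (14A.6) uses Reference only.

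**The case against.** The best defence is that both lists belong to one document and neither is worded as exclusive. Obeying 9.1 never breaches 14A, so this is an omission from the worksheet, not a clash. That is logically right. But the plan nowhere says that the stricter list governs, and the omission is on the page used at the bedside.

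A second defence is that Reference is the independent safety measure, and every other glucose stop uses it alone (9.1 items 3 to 5, 14A.3 to 14A.5, 9.2 items 1 and 2, 4.3.11). On that view 9.1 item 6 is the exception. This stands as far as it goes: either alignment removes the conflict, and the direction is a choice. A reader might count the ketone paragraph and the notification note as further support for CGM or Reference. Neither is a stop rule, so the fair count is two to one.

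Third, the safety effect is modest. Divergence needs a CGM that reads above Reference. The controller acts on CGM values, so over-reading tends to raise insulin delivery, not withhold it. The 30-minute checks, the ketone screen in 4.3.10, team notification and the shared 240 mg/dL stop all remain. Ketones above 1 mmol/L with Reference above 240 end the session under both lists. These points stand and keep the severity low. They do not say whether the session ends at the hour.

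Finally, list A speaks of signs of HHS and list B of an episode. A reader might infer that one subject meeting 14A.6 closes the whole study. The documents do not support that: 14A.4 and 14A.5 use the same signs wording for single-subject stops, and 4.3.12 puts HHS much higher. The label invites the misreading but does not establish it.

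**Conclusion.** The inconsistency is real and in current text. It is an internal inconsistency, minor to should-fix. Two staff members following different sections could treat the same valid readings differently for up to about 60 minutes. Under a steady rise of 1 to 2 mg/dL/min the figures are about 19 to 39 minutes at ratio 1.148, 25 to 50 at 1.20 and 7 to 14 at 1.05.

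A reader who compares 9.1 only with the 240 mg/dL stop might infer longer gaps at the faster rise. That overlooks 14A.6 itself firing once Reference has been above 300 for an hour.

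The rates of rise and the constant ratios are assumptions. The bound also assumes an in-tolerance CGM and a Reference that stays above 240 until a Protocol 2 stop fires. If Reference falls back first, Protocol 2 lets the session run on although 9.1 would have ended it. The size also depends on which CGM value counts, which 9.1 does not say.

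**What to change.** - Reword 14A.6 to match 9.1 item 6: "CGM or Reference Glucose Value remains > 300 mg/dL for more than 1 hour". This is the more protective version and needs one line changed.
- In both places, state which CGM value counts: either sensor, both, or the average used by FUSION.
- Remove the definition of signs of HHS from 14A.6. Reword item 13E so that it refers to this stop as mitigation of HHS risk, and say that meeting it does not by itself count as an HHS episode under 9.2 item 4 or 14B.4.

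The cost is a wording amendment with no new data or procedures. The downside is that a session may occasionally end on a CGM that over-reads, either within tolerance or while awaiting recalibration or replacement, and that subject cannot be replaced. Section 9.1 already accepts this.

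As a separate minor clarification, the whole-study DKA stop (9.2 item 3, 14B.3) could point to the DKA definition in 10.3.3.1 item 8.
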